## **Study Progression**

Part 1 of the study will be open-label. The study will begin with enrollment of approximately 375 participants in the 6 years to < 12 years age group (Study Arm 1) and dosing with 50 µg of mRNA-1273. After at least 75 participants in Study Arm 1 have completed Day 8 (1 week after Dose 1 of mRNA-1273 50 µg), an internal safety team (IST) will review the available safety data and provide a recommendation whether to escalate the dose to 100 µg in the 6 years to < 12 years age group (Study Arm 2; n = 375) and independently whether to begin dosing at the 50-µg dose level in the 2 years to < 6 years age group (Study Arm 3; n = 75). After at least 75 participants in Study Arm 1 reach Day 36 (1 week after Dose 2 of mRNA-1273 50 µg), the IST will again review the available safety data and provide a recommendation whether to administer Dose 2 of mRNA-1273 100 µg in Study Arm 2 and whether to administer Dose 2 of mRNA-1273 50 µg in Study Arm 3. Simultaneously, the enrollment of the remaining 300 planned participants for both Study Arm 1 and Study Arm 2 will be ongoing. A preliminary safety and immunogenicity data review of Study Arm 1, and Study Arm 2 as applicable, will aid in the selection of a dose level for Part 2. Once all or a subset of participants from each of Study Arms 1 and 2 reach Day 57 (1 month after Dose 2 of mRNA-1273), an interim analysis may be conducted to review the safety and immunogenicity data. Cumulative safety data for approximately 300 participants at the selected dose level will be reviewed by the Data Safety Monitoring Board (DSMB) before enrollment in Part 2, and the DSMB safety review recommendation will enable the expansion of the 6 years to < 12 years age group (Part 2) to receive either mRNA-1273 at the selected dose level (Study Arm 8; n = 3,000) or placebo (Study Arm 9; n = 1,000). The primary analysis of immunogenicity in Part 2 for Study Arm 8 (mRNA-1273 recipients) will be conducted after the pre-specified Immunogenicity Subset of participants reaches Day 57, and safety analysis will be conducted after a subset or all participants in Study Arms 8 and 9 reach Day 57.

Part 3 of the study will be open-label. A total of approximately 300 participants in the 6 year to < 12 year old age group will be enrolled to receive 3 total doses of mRNA-1273 at 25 µg, given as the primary series doses at Day 1 and Day 29 followed by a third dose on Day 149/booster dose (BD)-Day 1 (at least 3 months and up to 5 months after the second dose in the primary series). The primary analysis of immunogenicity and safety in Part 3 for Study Arm 14 will be conducted after all treated participants reach Day 57 (for primary series). The primary analysis of immunogenicity and safety for the third dose will be conducted after all participants who received a third dose reach Day 177/BD-Day 29.

For the middle age group (2 years to < 6 years), progression in Part 1 will be as follows: After 75 participants in Study Arm 3 have completed Day 8 (1 week after Dose 1 of mRNA-1273 50 µg), an IST will review the available safety data and provide a recommendation whether to

escalate the dose to 100 µg in the 2 years to < 6 years age group (Study Arm 4; n = 75) and whether to begin dosing in the 6 months to < 2 years age group at the 25-µg dose level (Study Arm 5; n = 150). After the 75 participants in Study Arm 3 reach Day 36 (1 week after Dose 2 of mRNA-1273 50 µg), the IST will review the available safety data and provide a recommendation whether to administer Dose 2 of mRNA-1273 100 µg in Study Arm 4 and whether to administer Dose 2 of mRNA-1273 25 µg in Study Arm 5. An optional Arm 7 may be enrolled in this age group (approximately 75 participants) at the 25-µg dose if the 100-µg dose is eliminated at any point during dose-escalation process, to maintain dose ranging for this age group. A preliminary safety and immunogenicity data review of all applicable arms will aid in the selection of a dose level for Part 2. Once all or a subset of participants in all applicable arms reach Day 57 (1 month after Dose 2 of mRNA-1273), an interim analysis may be conducted to review safety and immunogenicity data. A preliminary safety and immunogenicity data review of all applicable Arms will aid in the selection of a dose level for Part 2 and for expansion of the 2 years to < 6 years age group (Part 2) to receive either mRNA-1273 at the selected dose level (Study Arm 10; n = up to 3,000) or placebo (Study Arm 11; n = up to 1,000). The primary analysis of immunogenicity in Part 2 for Study Arm 10 (mRNA-1273 recipients) will be conducted after a pre-specified Immunogenicity Subset of participants reaches Day 57, and safety analysis will be conducted after a subset or all participants in Study Arms 10 and 11 reach Day 57.

For the youngest age group (6 months to < 2 years) progression in Part 1 will be as follows: In Study Arm 5, after 150 participants have completed Day 8 (1 week after Dose 1 of mRNA-1273 25 µg), an IST will review the available safety data and provide a recommendation whether to escalate the dose to 50 µg (Study Arm 6; n = 150). After the 150 participants in Study Arm 5 reach Day 36 (1 week after Dose 2 of mRNA-1273 25 µg), the IST will review the available safety data and provide a recommendation whether to administer Dose 2 of mRNA-1273 50 µg in Study Arm 6. Once all or a subset of participants in Study Arms 5 and 6 reach Day 57 (1 month after Dose 2 of mRNA-1273), an interim analysis may be conducted to review the tolerability and immunogenicity data at each dose level. A preliminary safety and immunogenicity data review of Study Arm 5 and Study Arm 6, as applicable, will aid in the selection of a dose level for Part 2 and allow for expansion of the 6 months to < 2 years age group (Part 2) to receive either mRNA-1273 at the selected dose level (Study Arm 12; n = up to 3,000) or placebo (Study Arm 13; n = up to 1,000). The primary analysis of immunogenicity in Part 2 for Study Arm 12 (mRNA-1273 recipients) will be conducted after the pre-specified Immunogenicity Subset of participants reaches Day 57, and safety analysis will be conducted after a subset or all participants in Study Arms 12 and 13 reach Day 57.

In general, if a decision is made not to proceed with administration of the higher dose and/or the second injection at a given dose level (eg, due to safety concerns), the participants scheduled to receive the higher dose may receive a lower dose, and the participants who had received the

higher dose level as their first injection will likely be given the next lower dose level that was tolerated for their second injection. The dose level not tolerated in the older age group will not be administered in any of the younger age groups. Within an age group, if one of the dose levels is found to have an unacceptable tolerability profile, the age group may progress to Part 2 at a lower dose level.

Part 1 and Part 2 participants who have not yet received a booster dose with mRNA-1273, nor a non-study vaccine booster dose will be offered an optional booster dose lower than the chosen primary series for each age group ([Table 4](#)), at least 3 months after Dose 2 of mRNA-1273.

The final analysis will be performed when participants (Study Arms 1 to 14) conclude the safety follow-up at 12 months after their last dose (either Dose 2 or booster dose).

The goal of the study is to support an indication for use of mRNA-1273 50 or 100 µg IM, given as 2 injections, approximately 28 days apart (pandemic dosing) or for the use of mRNA-1273 25 µg given as 3 injections, approximately 28 days (primary series) and at least 3 months and up to 5 months (third dose) apart (lower dosing) in the 6 years to < 12 years age group; mRNA-1273 25, 50, or 100 µg IM, given as 2 injections, approximately 28 days apart in the 2 years to < 6 years age group; and mRNA-1273 25 or 50 µg IM, given as 2 injections, approximately 28 days apart in the 6 months to < 2 years age group. In addition, the study will provide support for the indication of a booster dose, given at the lower dosage level of the primary series, at least 6 months, (as applicable), after Dose 2. The basis for demonstrating vaccine effectiveness is proposed to be met by measuring serum antibody responses in the study participants. The approach to inferring vaccine effectiveness will depend on whether an accepted serum antibody threshold conferring protection against COVID-19 has been established. If an antibody threshold of protection has been established, effectiveness will be inferred based on the proportion of study participants with serum antibody levels (on Day 57) that meet or exceed the antibody threshold. If an antibody threshold of protection has not been established, effectiveness will be inferred by demonstrating noninferiority for each age group (6 years to < 12 years, 2 years to < 6 years, and 6 months to < 2 years in Study P204) compared with young adult (18 to 25 years of age) participants enrolled in the ongoing clinical endpoint efficacy trial (Study P301) by both geometric mean (GM) values and seroresponse rate (SRR). The statistical parameters to infer effectiveness are described in [Section 2](#).

This study in children 6 months to < 12 years of age will monitor all participants for a total of 12 months following the second dose of vaccine or placebo, or 12 months following their booster or third dose, if applicable. If a COVID-19 vaccine is authorized or licensed for a specific age group before the end of the study, please refer to [Section 3.3](#) for unblinding and/or cross-over plans. Safety assessments will include solicited ARs 7 days after each injection (ie, the day of injection and 6 subsequent days), unsolicited AEs (28 days after each injection), and medically

attended adverse events (MAAEs), SAEs, and adverse events of special interest (AESIs) (including MIS-C and myocarditis and/or pericarditis) through the entire study period.

Blood samples will be collected from participants in Part 1, Part 2, and Part 3 of the study for assessment of immunogenicity as specified in [Section 3.1.1.2](#). If a Day 1 (baseline) blood sample cannot be obtained in either Part 1, Part 2, or Part 3, the participant will be considered either a screen failure due to inability to satisfy inclusion criterion 3 or could be rescheduled for rescreening. Participants may be rescreened 1 time, either within the same screening period for Part 1 or Part 2 or in a new screening period of Part 2 or Part 3 if the initial screening was in Part 1 or Part 2, respectively. If the participant is rescreened and a blood sample still cannot be obtained, then he/she will be considered a screen failure due to inability to satisfy inclusion criterion 3. Blood samples will also be tested for the development of antibodies directed against nonvaccine antigen (eg, antibodies against the nucleocapsid protein), which will signify infection with SARS-CoV-2. The incidence of SARS-CoV-2 infection among vaccine recipients and placebo recipients will be compared to assess the potential for mRNA-1273 to reduce the rate of infection in vaccine recipients. In addition, all participants will be monitored for symptoms of COVID-19 and scheduled for illness visits if concerning symptoms occur, and a nasal swab will be collected at the illness visit while Part 2 of the trial is still blinded for any age group. Once the trial is unblinded for all age groups and thus no placebo comparator group is available going forward, illness visits for COVID-19 symptoms or exposures and convalescent visits will no longer be required.

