The final analysis will be performed when participants (Study Arms 1 to 14) conclude the safety follow-up at 12 months after their last dose (either Dose 2 or booster dose).

The goal of the study is to support an indication for use of mRNA-1273 50 or 100 µg IM, given as 2 injections, approximately 28 days apart (pandemic dosing) or for the use of mRNA-1273 25 µg given as 3 injections, approximately 28 days (primary series) and at least 3 months and up to 5 months (third dose) apart (lower dosing) in the 6 years to < 12 years age group; mRNA-1273 25, 50, or 100 µg IM, given as 2 injections, approximately 28 days apart in the 2 years to < 6 years age group; and mRNA-1273 25 or 50 µg IM, given as 2 injections, approximately 28 days apart in the 6 months to < 2 years age group. In addition, the study will provide support for the indication of a booster dose, given at the lower dosage level of the primary series, at least 6 months, as applicable, after Dose 2. The basis for demonstrating vaccine effectiveness is proposed to be met by measuring serum antibody responses in the study participants. The approach to inferring vaccine effectiveness will depend on whether an accepted serum antibody threshold conferring protection against coronavirus disease 2019 (COVID-19) has been established. If an antibody threshold of protection has been established, effectiveness will be inferred based on the proportion of study participants with serum

---

---

antibody levels (on Day 57) that meet or exceed the antibody threshold. If an antibody threshold of protection has not been established, effectiveness will be inferred by demonstrating noninferiority for each age group (6 years to < 12 years, 2 years to < 6 years, and 6 months to < 2 years in Study P204) compared with young adult (18 to 25 years of age) participants enrolled in the ongoing clinical endpoint efficacy trial (Study P301) by both geometric mean (GM) values and seroresponse rate (SRR).

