This study in children 6 months to < 12 years of age will monitor all participants for a total of 12 months following the second dose of vaccine or placebo, or 12 months following their booster dose or third dose, if applicable. Safety assessments will include solicited adverse reactions (ARs) 7 days after each injection (ie, the day of injection and 6 subsequent days), unsolicited AEs (28 days after each injection), and medically attended adverse events (MAAEs), serious adverse events (SAEs), and adverse events of special interest (AESIs) (including multisystem inflammatory syndrome in children [MIS-C] and myocarditis and/or pericarditis) through the entire study period.

Blood samples will be collected from participants in Part 1, Part 2, and Part 3 of the study for assessment of immunogenicity. If a Day 1 (baseline) blood sample cannot be obtained in either Part 1, Part 2, or Part 3, the participant will be considered either a screen failure due to inability to satisfy inclusion criterion 3 or could be rescheduled for rescreening. Participants may be rescreened 1 time, either within the same screening period for Part 1 or Part 2 or in a new screening period of Part 2 or Part 3 if the initial screening was in Part 1 or Part 2, respectively. If the participant is rescreened and a blood sample still cannot be obtained, then he/she will be considered a screen failure due to inability to satisfy inclusion criterion 3. Blood samples will also be tested for the development of antibodies directed against nonvaccine antigen (eg, antibodies against the nucleocapsid protein), which will signify infection with severe acute respiratory syndrome coronavirus 2 (SARS-CoV-2). The incidence of SARS-CoV-2 infection among vaccine recipients and placebo recipients will be compared to assess the potential for mRNA-1273 to reduce the rate of infection in vaccine recipients. In addition, all participants will be monitored for symptoms of COVID-19 and scheduled for illness visits if concerning symptoms occur, and a nasal swab will be collected at the illness visit while Part 2 remains blinded for any age group. Once the trial is unblinded for all age groups and thus no placebo comparator group is available going forward, illness visits for COVID-19 symptoms or exposures and convalescent visits will no longer be required.

---

---

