**Table 1: Age Groups and mRNA-1273 Primary Series Dose Levels**

Age Group	mRNA-1273 Dose Levels Planned to be Evaluated
6 years to < 12 years	25  , 50, and 100 µg
2 years to < 6 years	25  , 50, and 100 µg
6 months to < 2 years	25 and 50 µg

Abbreviations: mRNA = messenger RNA.

 For Part 3, the 25-µg dose will be evaluated as an alternative (lower dose) dosing regimen with a primary series (2 doses) followed by a third dose (1 dose)

 The 25-µg dose will be evaluated if 100 µg is eliminated at any point during the dose-escalation process to maintain dose ranging for this age group.

The study will be conducted in 3 parts. Part 1 of the study will be open-label and consist of dose-escalation and age de-escalation to select the dose for each age group. Part 2 of the study will be a placebo-controlled observer-blind evaluation of the selected dose in each age group. Part 3 of the study will be open-label and consist of an exploration of a lower dose for any age group given as a 3-dose regimen (primary series followed by a third dose).

Immunogenicity data from participants who receive the mRNA-1273 vaccine at the selected dose level will be used to infer vaccine effectiveness. All participants will be followed up for 12 months after receipt of the second injection or 12 months after their booster or third dose, if applicable, whichever is longer.

Safety will be monitored throughout the study ([Section 7.5](#)).

Given that the preliminary data from Phase 1 to 3 studies have shown no significant safety concerns and robust immunogenicity, mRNA-1273 may be used to address the current COVID-19 outbreak as a result of its uniquely rapid and scalable manufacturing process. In particular, a safe and effective vaccine against SARS-CoV-2 in children will help facilitate a return to school as an additional step towards normalization of daily activities.

Considering the lack of approved vaccines for COVID-19 for children < 5 years, the participants' risk of COVID-19 outside the study during a pandemic, and the nonclinical and clinical data to date, the Sponsor considers the potential benefits of participation to exceed the risks.

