### **3.1.1.2 Treatment and Follow-up Period**

On Day 1, after the completion of the scheduled assessments ([Table 12](#) and [Table 17](#)), participants will be administered a single IM dose of the IP mRNA-1273 (25, 50, or 100  $\mu$ g) or placebo. Placebo will be administered only to those participating in Part 2 of the study. The procedures for IP administration will be detailed in the mRNA-1273-P204 Pharmacy Manual. Participants will be closely monitored for safety and will remain at the study site for observation

for at least 30 minutes after dosing. On Day 29, the second dose of IP will be administered. If the visit for the second dose (Day 29) is disrupted and cannot be completed at Day 29 (+7 days) as a result of the COVID-19 pandemic (self-quarantine or disruption of study site activities following business continuity plans and/or local government mandates for “stay at home” or “shelter in place”), the visit window may be extended to Day 29 + 21 days. When the extended visit window is used, the remaining study visits should be rescheduled to follow the intervisit interval from the actual date of the second dose. Participants will be monitored for 12 months after the second dose of IP (or booster) or 12 months after their third dose (Part 3) of IP, if applicable and whichever is longer for safety, immunogenicity assessments, and biomarker samples.

To test for the presence of SARS-CoV-2 by RT-PCR, nasal swab samples will be collected before the injections on Day 1, Day 29, Day 43 (if applicable per SoA), Day 57, Day 209, and Day 394. For Part 3, participants will have a nasal swab sample collected before the injections on Day 1, Day 29, Day 57, Day 149/BD-Day 1, Day 177/BD-Day 29, Day 329/BD-Day 181, and Day 514/BD-Day 366, according to the schedule of assessments (SoA; [Table 12](#) and [Table 17](#)). Participants who test positive at baseline may receive Dose 2 as long as they remain asymptomatic at the time of dosing.

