## 7 STUDY ASSESSMENTS AND PROCEDURES

Before performing any study procedures, all potential participants and/or participants' parent(s)/LAR(s) will sign an ICF (as detailed in [Section 10.2.6](#)). Participants will undergo study procedures at the time points specified in the SoAs ([Section 10.1](#)). A participant can also be seen for an unscheduled visit at any time during the study. An unscheduled visit may be prompted by reactogenicity issues, illness visit criteria for COVID-19 (as applicable while Part 2 of study is still blinded for any age group), or new or ongoing AEs. The study site also has the discretion to make reminder telephone calls or send text messages to inform the participant and/or participant's parent(s)/LAR(s) about visits, review eDiary requirements, or follow-up on ongoing or outstanding issues.

In accordance with "FDA Guidance on Conduct of Clinical Trials of Medical Products during COVID-19 Public Health Emergency" ([DHHS 2020](#)), investigators may convert study site visits to home visits or telemedicine visits with the approval of the Sponsor. Such action should be taken to protect the safety and well-being of study participants and study site staff or to comply with state or municipal mandates.

General considerations for study assessments and procedures include the following:

- Protocol waivers or exemptions are not allowed. The study procedures and their timing must be followed as presented in in the SoAs ([Section 10.1](#)). Adherence to the study design requirements is essential and required for study conduct.
- Immediate safety concerns should be discussed with the Sponsor immediately upon occurrence or awareness to determine if the participant should continue study treatment or participation in the study.
- All screening evaluations must be completed and reviewed to confirm that potential participants meet all eligibility criteria. The investigator will maintain a screening log to record details of all participants screened and to confirm eligibility or record reasons for screening failure, as applicable.
- Procedures conducted as part of the participant's routine clinical management (eg, pregnancy test) and obtained before signing of the ICF may be utilized for screening or baseline assessments provided the procedures met the protocol-specified criteria and were performed within the time frame defined in in the SoAs ([Section 10.1](#)).

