## 10 SUPPORTING DOCUMENTATION AND OPERATIONAL CONSIDERATIONS

### 10.1 APPENDIX 1: Schedule of Assessments

The SoA for Study Arms 1 through 13 is presented in [Table 12](#). The SoA for participants who received an optional booster dose (for Parts 1 and 2) with mRNA-1273 under Protocol Amendment 7 is presented in [Table 15](#). For participants who choose to receive a booster dose with mRNA-1273.214 under Protocol Amendment 9, please see [Table 19](#) for the mRNA-1273.214 booster dose SoA. The SoA for Study Arm 14 is presented in [Table 17](#). The SoA for placebo recipient cross-over vaccination with mRNA-1273 if any COVID-19 vaccine is authorized or licensed for participant's age group or another unblinding trigger is reached ([Section 3.3](#)) is presented in [Table 13](#).

If a participant cannot attend a study site visit (scheduled or unscheduled), with the exception of Screening, Day 1, and Day 29, a home visit is acceptable if performed by appropriately delegated study site staff or a home healthcare service provided by the Sponsor ([Section 7](#)). If neither a participant visit to the study site nor a home visit to the participant is possible (with the aforementioned exceptions), a safety telephone call should be performed that includes the assessments scheduled for the safety telephone calls.

The blood sampling schedule for exploratory serology and CMI in Part 2 of the study is presented in [Table 14](#). For participants who received a booster dose under protocol Amendment 7, see [Table 16](#) for the booster dose phlebotomy schedule. The blood sampling schedule for participants opting for booster dose in Parts 1 and 2 is presented in [Table 16](#). The blood sampling for Part 3 of the study is presented in [Table 18](#).

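### The text sets 12 months of safety follow-up after a booster, but the schedule for mRNA-1273.214 recipients (Table 19) ends the study 180 days after it.

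*Protocol*

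**What the plan says.** The narrative gives one rule for everyone.

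- Section 1.2.3 follows all participants for "12 months after receipt of the second injection or 12 months after their booster or third dose, if applicable, whichever is longer".
- Section 3.1 (Study Progression) monitors all participants for 12 months after the second dose, or "12 months following their booster or third dose, if applicable". It ties the final analysis to the point when Study Arms 1 to 14 "conclude the safety follow-up at 12 months after their last dose (either Dose 2 or booster dose").
- Section 3.1.1.2 has participants "monitored for 12 months after the second dose of IP (or booster").
- The synopsis repeats both statements: "The final analysis will be performed when participants (Study Arms 1 to 14) conclude the safety follow-up at 12 months after their last dose", and follow-up of "12 months following their booster dose or third dose, if applicable".

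None of these makes an exception for mRNA-1273.214.

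The schedules say otherwise. Section 10.1 begins its routing sentence with "For participants who choose to receive a booster dose with mRNA-1273.214 under Protocol Amendment 9" and sends that group to Table 19. The header of Table 12 does the same. Section 7 makes the schedules binding: "The study procedures and their timing must be followed as presented in" the schedules of assessments. The last visit in Table 19 is BD-4, at BD-D181, labelled as end of study. Its safety calls stop at BD-D169.

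Two passages were not brought into line with Table 19. Its footnote 2 names a BD-6 visit at BD-D366 that the table does not contain. Section 3.1.1 sends every boosted Part 1 and Part 2 participant to Tables 15 and 16, whose titles restrict them to mRNA-1273 boosters under Amendment 7.

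**The concern.** The primary safety endpoints for mRNA-1273.214 in Table 2 (MAAEs, SAEs and AESIs) run for the whole study period. The text, including the benefit/risk conclusion, presents that period as 12 months after the booster. The schedule that sites must follow collects about 6.

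Two things follow. A reader of the benefit/risk section expects about twice the post-booster observation that will exist for this product. And the final-analysis condition in Section 3.1 and the synopsis can never be satisfied for mRNA-1273.214 recipients, because nobody on Table 19 reaches 12 months after the last dose.

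A smaller related point concerns the pause rules. Footnote 2 of Table 5 says that events after booster doses are counted separately, so booster recipients come under rules 4 and 5, which count Grade 3 or higher solicited reactions. Section 7.4.3 withdraws the eDiary after mRNA-1273.214 and limits reporting to reactions that are medically attended, serious or lead to discontinuation. Table 5 does not take account of this.

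**Working it through.** No sample-size or power formula applies. The check is day arithmetic on the schedules.

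**Inputs**

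- Table 15 (mRNA-1273 booster): last visit BD-6, 365 days after the booster.
- Table 19 (mRNA-1273.214 booster): last visit BD-4 at BD-D181, 180 days after the booster, window -3/+14 days.
- Table 12 (unboosted): Dose 2 at D29, last visit at D394.
- Sections 3.1 and 3.3: mRNA-1273.214 may be given from 3 months after Dose 2.
- Table 13 notes: for placebo recipients who cross over, the Day 394 visit is counted from the first placebo dose.

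**Does any booster schedule deliver the stated 12 months?** Table 15 does: BD-D366 minus BD-D1 = 365 days. Table 19 does not: BD-D181 minus BD-D1 = 180 days.

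**Shortfall after the booster.** 365 - 180 = 185 days, and 180/365 = 49.3% of the stated period is delivered. With the visit window, BD-4 falls 177 to 194 days after the booster, so the window does not close the gap.

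**Follow-up after Dose 2, child first given mRNA-1273.** Unboosted: 394 - 29 = 365 days. Boosted *b* days after Dose 2: *b* + 180 days. The two are equal at *b* = 365 - 180 = 185, so any earlier booster ends follow-up before 12 months after Dose 2.

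| Assumed length of 3 months (earliest booster) | End of study after Dose 2 | Short of 365 days by |
|---|---|---|
| 84 days | 264 days | 101 days |
| 90 days | 270 days | 95 days |
| 92 days | 272 days | 93 days |

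**The same comparison for a placebo cross-over child.** Assume cross-over at Day 209, the 6-month point after Dose 2 at which Section 3.3 allows unblinding of children under 6. The second mRNA-1273 dose is at 209 + 28 = Day 237.

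- Unboosted: the last visit stays at Day 394, so 394 - 237 = 157 days after that dose.
- Boosted 90 days later, at Day 327: Table 19 ends at 327 + 180 = Day 507, so 507 - 237 = 270 days.

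Here the booster lengthens follow-up. The break-even of 185 days therefore applies only to children first given mRNA-1273.

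**Which length is intended?** Section 8.6.1 allows an mRNA-1273.214 safety analysis once recipients have 6 months of follow-up, which fits Table 19. Sections 3.1.1 and the synopsis cap the duration with a booster at 24 months. For a booster near Day 394 (about month 13), a 12-month rule needs 13 + 12 = 25 months plus 1 month of screening, which is over the cap. Table 19 needs 13 + 6 = 19 plus 1, or 20 months. A booster given 3 months after Dose 2 fits under the cap either way: 1 + 1 + 3 + 12 = 17 months. The cap therefore points to 6 months only for late boosters.

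**The case against.** The best defence is that the operative rule is clear. Section 10.1 and the Table 12 header route these children to Table 19, Section 7 makes it binding, Section 3.4 defines the end of study by the schedules, and Sections 7.1 and 7.4.7 collect safety data according to them. On that view the 12-month sentences are carry-over wording that Amendment 9 did not update. This stands as an account of what sites will do. A reader might infer that the mRNA-1273.214 safety endpoints are undefined or that sites cannot tell which schedule applies; the routing does not support that. The defence does not correct the 12-month statements or the trigger in Section 3.1.

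Other stronger readings should also be set aside.

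- *Every boosted child is followed for less time than an unboosted one.* This is false for cross-over children, as shown above, and for anyone boosted 185 days or more after Dose 2.
- *The number affected is the planned size of Study Arms 10 to 13.* That is an enrolment ceiling for an optional booster and includes placebo places. It also omits unboosted children in Arms 1 to 9, whom Table 19 covers. The protocol does not give the number boosted.
- *Section 8.6.1 calls the 6-month analysis interim, so longer follow-up must be planned.* The same section also calls the primary immunogenicity analyses interim, so the label proves nothing.
- *Pause rules 4 and 5 have no input after mRNA-1273.214.* Reactions that are medically attended, serious or lead to discontinuation are still recorded (Section 7.4.3, Table 19 footnote 8). Input is reduced, not absent.
- *Six months is too short.* Nothing in the protocol establishes that, and it is not claimed here.

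**Conclusion.** The contradiction is real and lies within the current text. Sections 1.2.3, 3.1 and 3.1.1.2 and the synopsis state 12 months after a booster, while Table 19 delivers 180 days (177 to 194 with the window), about half. The final-analysis trigger in Section 3.1 and the synopsis cannot be met for mRNA-1273.214 recipients; the one in Section 8.6.2, completion of planned procedures, can. Children first given mRNA-1273 and boosted less than about 185 days after Dose 2 also miss 12 months after Dose 2, by about 95 days at the earliest permitted booster if 3 months is taken as 90 days.

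The conflict is limited to mRNA-1273.214: Table 15 and the Part 3 schedule do reach 12 months. It should be fixed because the length of safety follow-up is a figure that the benefit/risk conclusion and the final-analysis timing rely on. It does not touch any hypothesis, alpha or power. Six months is the more likely intention, but the protocol nowhere says so.

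**What to change.** If 6 months is intended:

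- In Sections 1.2.3, 3.1 and 3.1.1.2 and the synopsis, state that follow-up after mRNA-1273.214 ends at BD-D181 and may end before 12 months after Dose 2.
- Make the final-analysis trigger in Section 3.1 and the synopsis match Section 8.6.2, so that it rests on completing the applicable schedule.
- Delete BD-6/BD-D366 from Table 19 footnote 2.
- Cite Table 19 in Section 3.1.1 for mRNA-1273.214, next to Tables 15 and 16 for mRNA-1273 boosters.

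The cost is amendment wording only.

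If 12 months is intended, extend Table 19 to BD-D366 on the Table 15 pattern, and revise the 24-month cap where late boosters would exceed it. The cost is two further contacts per recipient: a safety call at 270 days and a clinic visit at 365 days.

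In either case, add a note to Table 5 that rules 4 and 5 have only reduced input after mRNA-1273.214. Their 5% and 10% thresholds are then not meaningful, and pausing rests on rules 1 to 3, and on rule 6 for the events that Table 19 records.
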